## 4.3 Recruitment

\* Flow diagram according to Consort Statement for transparent reporting of randomized clinical trials.

\*\* End points after 1 and 12 months are secondary and were not part of the determination of sample size.

## 4.4 Withdrawal/follow-up

An already accepted patient is withdrawn from the study if the patient withdraws his consent. The study nurse records these events and reports them to the principal investigator. There are three follow-ups planned. The 6-months follow-up is the main one collecting data for both primary and secondary endpoints. The 1-month and 12 months follow-up are only collecting data for secondary endpoints. It is estimated that 35% of the included patients in every group will be lost for the 6-months follow-up. In case of acute suicidality during the follow-up telephone interviews the interviewers will be advised to stop the interview and contact professional help by use of a second phone.

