## 2 Study Methods

### 2.1 Trial design

The trial will be conducted as a multicentric, three-arm, observer-blinded, randomised control study under GP conditions. After depression screening using the PHQ-9 questionnaire eligible patients will be randomly put into one of three equally large study arms by specially programmed tablets administrated by a study nurse. Both patient-oriented plus GP feedback and feedback for the GP only after depression screening belong to the intervention whereas the no feedback arm belongs to the control group. At baseline patients directly fill in a questionnaire. The endpoints for the 1-, 6- and 12-months follow-up are collected via telephone interviews, which was already tested successfully in the preliminary study DEPSCREEN-INFO. The primary endpoint of this study is a change in the Patient health questionnaire-9 (PHQ-9) score for depression severity between baseline and the 6-months follow-up. The PHQ-9 is one of the most frequently used and best validated questionnaire for self-rating depressive conditions. It has the distinction of combining high sensitivity and specificity parameters and it is sensitive for changes considering depression treatment.

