### 4.2 Eligibility

A sample is eligible if the individual visits a GP's office with personal contact to the GP, is 18 years old or older, is acceptably proficient in German, consents to participate in the study and is suspected to have a depressive disorder, i.e. a PHQ-9 score greater than 9.

A sample is excluded if the individual has a life threatening health status, suffers from a severe somatic or/and psychological disorder that needs urgent treatment and is not currently diagnosed or treated for depressive disorder or shows an acute suicidal tendency as assessed with PHQ-9 Item 9. In addition, the sample will be excluded if the individual suffers from severe cognitive or/and visual difficulties, is not being able to fill out questionnaires or leaves no contact details.

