### 5.2 Analysis methods

#### 5.2.1 Analysis of primary endpoint

The primary outcome of all randomised patients will be analysed regarding the intention-to-treat principle and according to the memorandum of the DFG about good clinical practice all study results are going to be documented and published.

Primary outcome: depression severity (PHQ-9 score) 6 months after intervention as change from baseline. The primary outcome is going to be analysed via a mixed effects model including random effects patients and GP practices nested in centres and fixed factors for group and depression severity. The baseline comparisons will be represented by statistical contrasts. The use of the closure test ensures a familywise significance level of 5% if the p-value of the overall test is below 0.05.

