#### 5.2.3 Additional analysis

As additional exploratory analyses, subgroup analyses based on several demographic and clinical values are conducted w.r.t. change of PHQ-9 score. The aim of these analyses is to identify subpopulations, which benefit more or less from the intervention. These analyses shall give a first starting point for future studies. Missing values will not be imputed, but the implicit MAR assumption of the analysis model will be used.

The presented p-values are of descriptive nature only (two-sided tests at unadjusted significance level of 5%). The analyses are conducted in the FAS.

For the analyses on a potential interaction between the intervention and age (continuous, and categorical: young [ $\leq$ first tercile] vs. old [ $>$ third tercile]), sex (men vs. woman), depression history (previous episode vs. no history of depression), other mental health comorbidity (mental health comorbidity vs. mental health comorbidity), city size (ordinal), education ( $\leq$  10 years in school vs.  $>$  10 years in school), living situation (living together vs. alone), insurance status (private vs. statutory health insurance), reason for GP visit (psychological vs. physical), migration background (migration background vs. no migration background), quality of life at baseline (continuous and dichotomized with median as cut-off point; based on the visual analogue scale of the EQ-5D), anxiety disorder (yes vs. no), substance disorder (yes vs. no), chronic physical disease (yes vs. no), persistent somatic symptoms (yes vs. no), mood swings (yes vs. no), social support (yes vs no), pregnancy in female patients (yes vs. no) and breast feeding in female patients (yes vs. no) on the change in PHQ-9 score from baseline to month 6, the regression models and their parameters are defined analogously to the primary analyses but additional effects for demographic and clinical values and its interaction with the treatment are added to each model.

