### 5.3 Missing data

The mixed effects model as chosen model class is comparatively robust regarding missing data. In addition an analysis using multiple imputation of missing data in baseline variables will be performed as sensitivity analysis.

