### 5.4 Harms

There is no evidence that feedback concerning depression severity causes suicidality or self-harm; it rather seems that questions of suicidality lower the risk of suicide. To guarantee a safe handling with suicidality any evidence of acute suicidality leads to the immediate information of the GP in every of the three study conditions (including the NO-FEEDBACK condition). If acute suicidality is confirmed by the GP a locally coordinated emergency plan in cooperation with the GPs and centres of psychiatry or rather psychosomatic medicine is introduced. In case of suicidal patients blinding is abolished, treatment is introduced and these patients are excluded from the study. Main risks and obstacles during performing of the study are negative events for the patients. For that reason a suitable monitoring is installed. Monitoring and supervision is being controlled by a specialised company (e.g. Clinical Trials Center (CTC) North). A data handling plan agreeing the DFG guidelines and the Federal Data

Protection Act is going to be published beforehand and ensures data availability, transparency and repeatability. Furthermore, the study follows international guidelines such as ICH-GCP (CHMP, 2016) as well as the guidelines and SOPs of the University Medical Centre Hamburg-Eppendorf.

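### A 6-month PHQ-9 may be missing, or be dropped, because of acute suicidality, and no planned analysis tests that loss

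*SAP*

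**What the plan says.** The primary outcome (SAP 5.2.1) is "depression severity (PHQ-9 score) 6 months after intervention as change from baseline". Section 2.1 says how it is obtained: "The endpoints for the 1-, 6- and 12-months follow-up are collected via telephone interviews".

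Two sections deal with suicidality after entry. Section 4.4 states: "In case of acute suicidality during the follow-up telephone interviews the interviewers will be advised to stop the interview". Section 5.4 states: "In case of suicidal patients blinding is abolished, treatment is introduced and these patients are excluded from the study". Section 4.4 gives withdrawal of consent as the only reason for withdrawing a patient, and section 3.3.1 defines the ITT population as everyone randomised.

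Section 5.3 covers missing data in two sentences. The first reads: "The mixed effects model as chosen model class is comparatively robust regarding missing data". The second says that "an analysis using multiple imputation of missing data in baseline variables will be performed as sensitivity analysis". The assumption behind the model is named only in section 5.2.3, for the exploratory subgroup models, which are built like the primary one: "Missing values will not be imputed, but the implicit MAR assumption of the analysis model will be used".

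The SAP does not say how a PHQ-9 cut short by a stopped call is scored, or whether a score already obtained from a patient excluded under 5.4 is analysed.

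**The concern.** A likelihood-based mixed model gives valid estimates when missingness depends only on what has been observed: arm, baseline severity and any earlier scores in the model. A call stopped for acute suicidality is different. The reason for the stop is the patient's state at that call, which the PHQ-9 is meant to measure. If no score results, its absence can depend on the unseen value even after conditioning on the observed data. Imputing baseline variables does nothing about this.

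Section 5.4 opens a second route. An analyst who follows its wording could remove a score that was in fact recorded, although 3.3.1 would keep it.

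The scores concerned would be among the worst in the trial. If one arm loses more of them than another, the arm difference is distorted. If feedback lowers suicidality, the comparators lose more high scores and the benefit looks smaller. If feedback raises it, the harm looks smaller.

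**Working it through.** **Step 1. Does the text allow the loss?** Yes, by two routes.
- The outcome is collected by telephone (2.1), and that call is stopped for acute suicidality (4.4). If the stop comes before the PHQ-9 is complete, the total is missing.
- If the PHQ-9 is complete but 5.4 is applied literally, the score can be dropped.

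Neither 5.3 nor any other section plans an analysis that varies the missing-at-random assumption for the outcome.

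**Step 2. The plan's own figure.** Section 2.3 gives 233 per group for a three-group F-test at alpha 0.05, power 0.80 and group effects 0 and 0.25. With means 0, 0, 0.25 and SD 1:
- The grand mean is 0.0833, and the sum of squared deviations is 2 × 0.00694 + 0.02778 = 0.04167.
- The noncentrality is 233 × 0.04167 = 9.71, and the power is 0.801. This reproduces 233, hence 699.
- 1074 × 0.65 = 698.1, close to 699. The sample size is not in dispute.

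**Step 3. Illustrative size.** The SAP gives no rate of stopped calls and no excess score, so both are assumed here. Let q be the share of an arm whose 6-month score is lost through suicidality, and D how far those scores lie above the rest, in SD units. For observed-case means:

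bias in the contrast = (q in comparators − q in intervention) × D

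| q intervention | q each comparator | D | Bias (SD) | Share of 0.25 | Power at 233 per group |
|---|---|---|---|---|---|
| 1% | 1% | 1 to 2 | 0 | 0% | 0.80 |
| 1% | 2% | 1 | 0.01 | 4% | 0.77 |
| 1% | 2% | 2 | 0.02 | 8% | 0.73 |
| 1% | 3% | 1 | 0.02 | 8% | 0.73 |
| 1% | 3% | 2 | 0.04 | 16% | 0.64 |
| 2% | 5% | 1 | 0.03 | 12% | 0.69 |
| 2% | 5% | 2 | 0.06 | 24% | 0.55 |

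The first row assumes the same D in all arms. The power column holds 233 per group fixed and shrinks the 0.25 by the bias.

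**Step 4. Are such arm differences plausible?** Suppose severity is normal, calls stop above a fixed cut-off, and the intervention shifts severity by the planned 0.25 SD.
- A comparator rate of 3% becomes 1.66% (normal quantile 1.881 + 0.25 = 2.131), a difference of 1.34 percentage points.
- A rate of 5% becomes 2.91% (1.645 + 0.25 = 1.895), a difference of 2.09 points.

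With D of 1 to 2, the bias is 5 to 11% and 8 to 17% of 0.25. That lies inside the table's range but below its top.

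**Step 5. Scale against total loss.** Of 1074 / 3 = 358 included per arm, 358 × 0.35 = 125 are expected to be lost at 6 months. Rates of 1 to 5% among the 233 reached are about 2 to 12 patients per arm.

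**The case against.** A reader might infer that the highest scores will drop out of every arm mean. The SAP does not support that. Section 4.4 advises stopping the interview; it does not say that answers are discarded. The only link between the PHQ-9 and acute suicidality is in the eligibility criteria (4.2), which exclude a person who "shows an acute suicidal tendency as assessed with PHQ-9 Item 9". The SAP does not say how suicidality is detected at follow-up. If item 9 is the trigger there too, it is the last of nine items, so a scale asked in order would be complete when the call stops. Under 3.3.1 and 5.2.1 that score would ordinarily be analysed. This part of the objection stands: loss is a possibility.

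A reader might also infer that 5.3 itself assumes missing at random. It does not say so. The assumption is stated in 5.2.3 for exploratory models and carries over because those models are defined by analogy with the primary one.

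The size is hypothetical. Acutely suicidal patients are excluded at entry, which should make later stops rarer. The model conditions on baseline severity and, if the 1-month score enters it, on that as well, so part of the bias could be recovered. The order of instruments in the call is a matter of conduct that the protocol may settle, and it is not criticised here.

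The objection does not remove two things. Section 5.4 gives an analyst a textual basis for dropping an obtained score, against 3.3.1. And the missing-data section contains no check on a missing outcome, although the SAP itself describes a way in which the outcome could be missing because of its value.

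**Conclusion.** The point holds in a limited form. Under 4.4 and 5.4 a 6-month PHQ-9 may be missing, or be removed, for a reason tied to its own value, and 5.3 contains nothing that would show whether this matters.

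The number of such patients is unknown and probably small beside the expected 35% loss. The arm contrast is biased only if the stops, or the scores lost through them, differ by arm. Assuming 1 to 2% lost in the intervention arm, 2 to 5% in each comparator and scores 1 to 2 SD above the rest, the contrast shrinks by 0.01 to 0.06 SD, or 4 to 24% of the planned effect. With equal rates and equal excess scores it does not shrink at all. These are observed-case figures on assumed inputs, not a forecast.

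This does not invalidate the primary analysis. It is a cheap improvement to the plan. The safety procedure is not questioned.

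**What to change.** Leave the safety procedure as it is and make three changes to the SAP.

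1. **Keep what was answered.** State in 4.4 and 5.3 that PHQ-9 answers obtained before a call is stopped are retained, scored by a prespecified rule for incomplete scales, and analysed as observed under ITT. Reconcile the exclusion in 5.4 with the ITT definition in 3.3.1 and with the withdrawal rule in 4.4, so that it is clear whether leaving the study also means leaving the analysis.
2. **Test the assumption on the outcome.** Add a missing-not-at-random sensitivity analysis of the 6-month PHQ-9, for example delta-adjusted multiple imputation over a stated range of shifts, with an unfavourable shift for stopped calls without a scorable PHQ-9. A range is preferable to one fixed unfavourable value, which would be arbitrary. The same analysis would serve the wider 35% loss.
3. **Report the events.** Tabulate stopped calls by arm and visit, with the number that yielded a scorable PHQ-9.

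The cost is a few lines of wording, a few prorated scores and one extra sensitivity analysis.

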## 4.5 Baseline patient characteristics

Every patient is invited to the study via the study nurse. The patient consents to participate in the study and receives a depression screening.

The baseline patient characteristics will be summarised in an electronic case-report form (eCRF). As descriptive measures absolute and relative frequencies (for categorical variables), median and quartiles (for skewed-distributed variables), and mean and standard deviations (for variables with assumed normal distribution) are calculated. Appropriate graphics will be used for illustration of the results.

## 5 Analysis

### 5.1 Outcome definitions

Primary outcome: depression severity 6 months after intervention measured by the PHQ-9 score.

### 5.2 Analysis methods

#### 5.2.1 Analysis of primary endpoint

The primary outcome of all randomised patients will be analysed regarding the intention-to-treat principle and according to the memorandum of the DFG about good clinical practice all study results are going to be documented and published.

Primary outcome: depression severity (PHQ-9 score) 6 months after intervention as change from baseline. The primary outcome is going to be analysed via a mixed effects model including random effects patients and GP practices nested in centres and fixed factors for group and depression severity. The baseline comparisons will be represented by statistical contrasts. The use of the closure test ensures a familywise significance level of 5% if the p-value of the overall test is below 0.05.

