## 1.2 Objectives

This trial is conducted to primarily determine the efficacy of a widely available feedback intervention after depression screening for depressive symptomology in six months as well as costs, depression severity after 1 and 12 months, diagnosis of depression (MINI), anxiety (GAD-7), somatic symptom severity (SSS-8) and quality-adjusted life years as secondary endpoints. Primary hypothesis: patient-oriented electronic depression feedback (including GP feedback) leads to a lower depression severity (PHQ-9) after 6 months compared to both GP feedback and no feedback at all. Secondary hypothesis: patient-oriented feedback after depression screening is more cost efficient after 6 months compared to both GP feedback and no feedback at all caused by a reduction of health costs (CSSRI). Furthermore, the influence

of Germany's first implementation of a depression screening on routine care of primary medical patients is evaluated.

The primary and secondary endpoints are in detail (Table 1 in the approval):

Instruments	Measurement			
	Baseline	1-month follow-up	6-months follow-up	12-months follow-up
Primary Endpoint				
Depression severity (PHQ-9)	x	x	x	x
Secondary Endpoint				
Clinical scales (Anxiety severity, GAD-7, somatic symptom severity, SSS-8, quality of life, EQ5D)	x	x	x	x
Patient knowledge and behavior regarding guideline recommendations (e.g., adherence, coping, search for information)			x	x
Health care use (e.g., doctor consultations, medication) (CSSRI)			x	x
Mini-International Neuropsychiatric Interview (MINI)		x	x	x
Patient activation (PAM13-D)			x	
Satisfaction and acceptance of screening and feedback (USE)			x	
Open questions (e.g., strategies in response to a diagnosis)				x
Medical record (i. e., diagnosis, treatment)	x		x	
Demographic information	x			

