### 2.2 Randomization

A randomising sequence is created (boxes for 97 patients with probabilities for each condition derived from estimated prevalences and two test entries – 999 total boxes) not being SAP **2.0**

accessible for neither study nurse nor GP at any given point. After a patient has finished the baseline measurement, reached a PHQ-9 score higher than 9, randomisation happens electronically (allocation concealment). Patients are stratified by their depression severity (moderate and severe). The study is not cluster-randomised, as within every single GP's office each of the three conditions is realised and therefore an individual randomisation of patients is feasible.

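### The primary model adjusts only for a two-level severity factor, not the continuous baseline PHQ-9, so precision is lost and the two stated outcome definitions can give different answers

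*SAP*

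**What the plan says.** The SAP describes the primary outcome in two ways.

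- **As a 6-month level.** Section 5.1 reads "Primary outcome: depression severity 6 months after intervention measured by the PHQ-9 score". The primary hypothesis in section 1.2 is also about a level: patient-oriented feedback "leads to a lower depression severity (PHQ-9) after 6 months compared to both GP feedback and no feedback at all".
- **As a change.** Section 2.1 reads "The primary endpoint of this study is a change in the Patient health questionnaire-9 (PHQ-9) score for depression severity between baseline and the 6-months follow-up", and section 5.2.1 reads "Primary outcome: depression severity (PHQ-9 score) 6 months after intervention as change from baseline". Sections 2.4 and 5.2.3 also refer to change.

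Section 5.2.1 describes the model as "including random effects patients and GP practices nested in centres and fixed factors for group and depression severity". It does not define the severity factor. The only definition is in section 2.2: "Patients are stratified by their depression severity (moderate and severe").

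Baseline PHQ-9 is available for everyone. Section 4.2 requires "a PHQ-9 score greater than 9", and section 2.2 places allocation after the score is known: "After a patient has finished the baseline measurement, reached a PHQ-9 score higher than 9, randomisation happens electronically". No section enters that score in the primary model as a continuous covariate. Section 5.2.2 promises adjusted and unadjusted means but does not name the adjustment variables.

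**The concern.** If baseline PHQ-9 is a linear covariate, it does not matter whether the outcome is the 6-month score or the change, because the group contrast is identical. If baseline enters only as moderate versus severe, that equivalence is lost. The two estimates then differ by the chance within-stratum difference between arms in baseline PHQ-9, and the SAP's two definitions leave room to report either.

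The second cost is precision. A plain change score assumes a slope of 1 for 6-month on baseline score, and a plain 6-month score assumes a slope of 0 within strata. Patients are selected for a high baseline, so regression to the mean makes a slope below 1 likely. That does not bias a randomised comparison, but it leaves baseline noise in the change score and widens the interval for the primary contrast.

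The choice also carries over. Secondary endpoints are analysed like the primary (section 5.2.2), and subgroup models are built by analogy with it (section 5.2.3).

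**Working it through.** **The plan's own figure.** Section 2.3 uses a three-group F-test with α = 0.05, power 0.80 and group effects 0 and 0.25, read as means 0, 0, 0.25 with SD 1. The noncentrality is λ = n·Σ(μᵢ − μ̄)² = 233 × 2 × 0.25² / 3 = 9.71, on 2 and 696 df. Power is 0.7996 at n = 232 and 0.8014 at n = 233, so 233 per group reproduces. The point below does not affect it.

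**Assumptions.** The SAP gives no SD, correlation, baseline distribution or severe cut-off. I take baseline PHQ-9 from 10 to 27 with geometrically decreasing frequencies, severe = 15 or more, 6-month SD 5 and correlation ρ from 0.2 to 0.6. Two baseline shapes are shown:

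| Severe | Baseline SD | Within-stratum variance Vw | Within-stratum SD | Vw as share of total |
|---|---|---|---|---|
| 32% | 3.73 | 4.31 | 2.08 | 31% |
| 39% | 4.18 | 5.48 | 2.34 | 31% |

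**Residual variance.** Write Y6 = a + bX + e, with b = ρ × 5 / SD(X) and Var(e) = 25(1 − ρ²).

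- Continuous baseline in the model: Var(e)
- Change with severity factor only: Var(e) + (b − 1)²·Vw
- Score with severity factor only: Var(e) + b²·Vw

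Example with 32% severe and ρ = 0.4: b = 0.4 × 5 / 3.73 = 0.536 and Var(e) = 21.0. The ratio for change is 1 + (0.464² × 4.31)/21.0 = 1.044. The ratio for score is 1 + (0.536² × 4.31)/21.0 = 1.059.

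Ratios to the baseline-adjusted model:

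| ρ | Change, 32% severe | Change, 39% severe | Score, 32% severe | Score, 39% severe |
|---|---|---|---|---|
| 0.2 | 1.10 | 1.13 | 1.01 | 1.01 |
| 0.3 | 1.07 | 1.10 | 1.03 | 1.03 |
| 0.4 | 1.04 | 1.07 | 1.06 | 1.06 |
| 0.5 | 1.03 | 1.05 | 1.10 | 1.11 |
| 0.6 | 1.01 | 1.03 | 1.17 | 1.18 |

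Change loses most at low correlation and score at high correlation. The adjusted model is at least as precise as either in every row.

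**In patients and power.** A ratio of 1.05 is worth 233 × 0.05 ≈ 12 patients per arm, and 1.10 is worth 233 × 0.10 ≈ 23. If d = 0.25 is on the severity-only scale, multiplying λ by 1.05 or 1.10 raises power from 0.801 to 0.821 or 0.840.

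**Gap between the two definitions.** With only the stratum in the model, the score and change estimates differ by the within-stratum baseline difference, whose SD is √(2·Vw/233).

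- 32% severe: √(2 × 4.31/233) = 0.192, so 1.96 × 0.192 = 0.38 points
- 39% severe: √(2 × 5.48/233) = 0.217, so 1.96 × 0.217 = 0.43 points

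The assumed effect is 0.25 × 5 = 1.25 points, so the 95% range of the gap is 30% to 34% of it.

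**Simulation check.** Two arms of 233, a true effect of 0.25 SD, 6-month SD about 5.5, ρ from 0.3 to 0.6, 4,000 trials per scenario. The SD of the gap was about 0.165. With the severity factor only, the two definitions fell on opposite sides of p = 0.05 in about 7% to 8% of trials. With continuous baseline added they never did, and the largest difference between estimates was 4 × 10⁻¹⁴.

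**The case against.** The strongest reply is that this is a modest efficiency preference joined to an editorial slip. Four sections say change, section 5.2.1 merges the two phrasings, and an analyst following that section would analyse change. Both definitions target the same mean group difference, and randomisation keeps either analysis unbiased with correct type I error. The severity factor already removes about two thirds of the baseline variance. Ratios of 1.01 to 1.13 widen the interval by only about 0.5% to 6% (√1.01 and √1.13). With a narrower baseline (SD 2.7, 17% severe) the loss for change falls close to zero at ρ = 0.5, and the gap shrinks to 1.96 × 0.145 ≈ ±0.28 points. By comparison, the effect's own 95% half-width at SD 5 is 1.96 × 5 × √(2/233) ≈ 0.91.

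All of that is fair on size, and it is why the point is not graded as essential. It does not remove the point. Section 5.1 is where the outcome is meant to be fixed, and it does not say change. A disagreement on significance in 7% to 8% of trials is avoidable.

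One could also read the patient random effect and the mention of baseline comparisons in section 5.2.1 as a repeated-measures model with baseline as an outcome. The SAP gives no visit term and writes the outcome as change, so the text does not support that reading.

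**Conclusion.** The concern holds and should be acted on. The text part is firm: two outcome definitions stand in the current SAP, and continuous baseline PHQ-9 is absent from the primary model. That the severity factor in section 5.2.1 has two levels is inferred from section 2.2, the only place that defines it.

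The size rests on the assumptions above. Residual variance of change is 1% to 13% higher than necessary (about 4% to 10% at correlations of 0.3 to 0.4), and the two definitions can differ by chance by about ±0.4 points, with about ±0.3 for a narrower baseline distribution. This is lost precision and an avoidable choice on the primary result. It is not bias, inflated type I error or a fault in the sample size.

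**What to change.** - In section 5.2.1, add baseline PHQ-9 as a continuous covariate and keep the severity stratum as the randomisation factor.
- State one outcome definition and use it in sections 1.2, 2.1, 2.4, 5.1, 5.2.1 and 5.2.3. With the covariate in place, either choice gives the same group contrast.
- If the follow-up visits are modelled jointly, as the patient random effect may intend, say so and add visit terms and a baseline-by-visit interaction.
- Do the same for GAD-7, SSS-8 and EQ-5D, which section 1.2 lists as measured at baseline, and name the adjustment variables behind the adjusted means in section 5.2.2.

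The cost is one model term and some aligned wording. No new data are needed, and because the score precedes randomisation no patient is lost for a missing covariate. The version history shows a signed final version 2.0, so the change needs a dated, documented amendment made before the group comparison is seen. If that is no longer possible, report the baseline-adjusted model as a declared sensitivity analysis.
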